##### *Specific Content Changes*

#### Protocol Approval Signature Page

- Replaced [name]., Senior Vice President, Clinical Development, with [name], PhD, Acting Chief Medical Officer, as a signatory.

#### Synopsis

- Added the following text to the Background and Study Rationale to align with the most recent IB, “across all patients was 21% and the clinical benefit rate (CBR) is 33%. Similar ORR were seen in the patients with “penta” and “quad” MM, with higher CBR in patients who received 8 vs. 6 doses/cycle consistent with improved disease control with continuous dosing.”
- Added the following text, “If any patient is not able to tolerate this dose, then a potential discontinuation or further decrease in dosage would be allowed after a discussion with the Medical Monitor on a case by case basis,” to allow for adjustments to the dosing of dexamethasone.

#### Inclusion/Exclusion Criteria (also in Synopsis and Sections 8.4 and 8.5)

- Modified inclusion criteria #10 to clarify that female patients of childbearing potential must agree to use 2 methods of contraception (including 1 highly effective and 1 effective method of contraception).
- Modified inclusion criteria #13 to remove “on Cycle 1 Day 1” for hemoglobin level  $\geq$  8.5 g/dL.

- Modified inclusion criteria #14 to add “key” to specific criteria.
- Corrected exclusion criteria #17 to add  $\geq$  to Grade 2 painful neuropathy

**Table 1 (Schedule of Assessments)** (also in Section 9.7.2.4)

- Modified footnote #8 to, “For females of childbearing potential; negative serum hCG pregnancy test must be obtained within 3 days before the first dose of study treatment. Pregnancy testing (serum hCG or urine) is also required for females of childbearing potential prior to dosing on Day 1 of Cycles  $\geq$  2 and at the EoT Visit (serum hCG). Pregnancy testing may also be performed as clinically indicated during the study,” to required that testing is performed on Day 1 of Cycles  $\geq$  2.

**List of Abbreviations:**

- Removed definition for FLC (kappa/lamba ratio) for clarification
- Added definition for TRAE (treatment-emergent adverse event)

**Protocol, Main Body**

**Section 4.3**

- Updated the clinical experience sections to the most recent safety and efficacy information for MM in the KCP-330-001 study and for KCP-330-012 study in the IB.

**Section 4.4**

- Updated the information on ACS to reflect the current selinexor safety information.

**Section 5.1**

- Added the following text, “If any patient is not able to tolerate this dose, then a potential discontinuation or further decrease in dosage would be allowed after a discussion with the Medical Monitor on a case by case basis,” to allow for adjustments to the dosing of dexamethasone.

**Section 9.2**

- Updated text to reflect IMWG requirement for sequential sample to confirm response, “SPEP with serum protein immunofixation, quantitative Ig, serum FLC, and 24-hour UPEP, with immunofixation, must be collected at each required time point. An aliquot of the blood and urine samples should be retained. If the local laboratory results indicate a CR or sCR, a sequential sample, per IMWG, should be collected and analyzed. Aliquots from the initial and subsequent collection will be sent to the central laboratory to confirm the CR or sCR response.”
- Corrected in Table 4 that karyotyping and FISH will be performed at a central laboratory, not a local laboratory.

CCI

### Section 9.3

- Updated text to specify that all MM assessments are required at each time point. Added text to clarify the timing of collection of sequential MM assessment samples, “Two consecutive samples are required to confirm the response. The time period between samples may be discussed with the Medical Monitor and can occur on the same day, as long as, the samples are analyzed separately.”

### Section 9.4.4

- Added new Section, Pregnancy Testing, with the following text: “For females of childbearing potential, a negative serum human chorionic gonadotropin (hCG) pregnancy test must be obtained within 3 days before the first dose of study treatment. Test sensitivity for hCG must be  $\geq 25$  mIU/mL. Pregnancy testing (serum hCG or urine) is also required for females of childbearing potential prior to dosing on Day 1 of Cycles  $\geq 2$  during the study and at the EoT Visit (serum hCG). Pregnancy testing may also be performed as clinically indicated during the study.”

### Sections 9.5.1, 9.7.2.1, 9.7.2.2 and Table 6

- Replaced text in these sections with, “As of protocol version 5.0, these samples are no longer collected.” Table 6 was removed as the PK CCI blood samples are no longer being collected as is it not necessary to continue collecting these samples.

CCI

– CCI

CCI

### Section 11.1.3

- Added the following text, “If any patient is not able to tolerate this dose, then a potential discontinuation or further decrease in dosage would be allowed after a discussion with the Medical Monitor on a case by case basis,” to allow for adjustments to the dosing of dexamethasone.

CCI

### Section 11.2 and Appendix 4

- Modified text to simplify the description of the blister packaging.

#### **Section 11.4.7**

- Revised Prevention of Pregnancy language to Contraception Requirements to clarify that female patients of childbearing potential must agree to use 2 methods of contraception (including 1 highly effective and 1 effective method of contraception).

#### **Section 12.1.3.1**

- Added the Karyopharm German PV fax number for European sites.
- Revise text to modify reporting suspected unexpected serious adverse reactions to the competent authorities and relevant ethics committees in accordance with the FDA’s “Safety Reporting Requirements for Investigational New Drugs and Bioanalytical/Bioequivalence Studies” or as per national regulatory requirements in participating countries in order to ensure safety information is reported to authorities in all countries participating in the study.

#### **Section 14.11**

- Clarified the publication language to include the following text, “Publication will be in a relevant peer- reviewed journal, with authorship status and ranking designated according to the acknowledged contributions of participating investigators, institutions and the Sponsor.”

#### **Section 15**

- Added Vogl 2016 to the list of references

#### **Appendix 7:**

- Revised Changes to the Protocol for Protocol Version 4.1 to accurately capture changes made to that version of the protocol.

## Amendment 5

### Protocol Version 6.0

#### Amendment Rationale

The primary purpose for this amendment was to update statistical language (e.g., definition of analysis populations, CCI [REDACTED]) and to address inconsistencies.

The revised protocol Version 6.0 dated 13 December 2017 will be submitted by the Principal Investigator(s) to all applicable Institutional Review Boards (IRBs), Independent Ethics Committees (IECs), or Research Ethics Boards (REBs), and by Karyopharm Therapeutics Inc. to all applicable Regulatory Authorities.

A summary of key changes that were made to protocol Version 5.0, including rationales for these changes, is provided below.

#### Changes to the Protocol

##### *Administrative Changes*

- Updated the version number and date of protocol (**Modified sections:** Global)
- Internal changes to improve clarity (Modified sections: Global)

##### *Specific Content Changes*

#### Protocol Approval Signature Page

- Replaced [name], PhD, Acting Chief Medical Officer, with [name] [name], Vice President, Clinical Strategy, as a signatory.

#### Synopsis

- Objectives: updated for consistency with the Statistical Analysis Plan:
  - Updated definitions of Durations of CBR and DCR.  
CCI [REDACTED]
- Statistical Methods: updated the definition of mITT and PP populations, for consistency with SAP, CCI [REDACTED].

#### Table 1 (Schedule of Assessments) (also in Section 9.2)

- Modified footnotes #2 and #9 to indicate that results of pre-screening MM assessments at Day -30 (window: Screening – 2 weeks) and Day -60 (±15 days) will be provided. This information is required to more fully understand history of patient's MM (extent of disease, rate of progression).

#### Protocol, Main Body

##### Section 4.1

- Updated the Introduction for clarity and accuracy.

##### Section 6.2

- Updated definitions of Durations of CBR and DCR, for consistency with the SAP.

### Section 7.3

- Deleted the following text, as IRC does not review disease assessments at the time of progression and discontinuation of treatment does not require confirmation of PD by IRC: “...and must review at time of progression. Progression based on site generated disease assessment data must be confirmed by the IRC prior to discontinuing treatment.”.

### Section 8.2

- Removed Canada from the list of countries where the study is being conducted, to reflect that the study is not being conducted in Canada.

### Section 8.8

- Added the following text after date of birth, “(as allowed by regulatory authorities)” to clarify that investigator should provide birth date information in compliance with their regulatory authorities.

### Section 9.1.2, 9.2

- Added text to indicate that results of pre-screening MM assessments at Day -30 (window: Screening – 2 weeks) and Day -60 ( $\pm 15$  days) will be provided. This information is required to more fully understand history of patient’s MM (extent of disease, rate of progression).
- Text edited in Section 9.2 to clarify sample collection and analysis procedures in the event of a CR or sCR, to align with the lab manual.

CCI

█

CCI

█

### Section 13.2.1

- For consistency with Statistical Analysis Plan:
    - Updated the definition of mITT and PP populations
- █ CCI
- Updated Sub-group Efficacy Analyses

### Section 13.3.4

- Updated the definition of mITT and PP populations, CCI for consistency with Statistical Analysis Plan.

**Appendix 7:**

- Added Summary of Changes for Protocol Version 6.0 to describe changes made to version 5.0.

ETDRS	Early Treatment Diabetic Retinopathy Study	sCR	stringent complete response
FACT-G	Functional Assessment of Cancer Therapy – General	SD	stable disease
FACT-MM	Functional Assessment of Cancer Therapy – Multiple Myeloma	Sd	selinexor 80 mg plus dexamethasone 20 mg ("low-dose" dexamethasone)
FISH	fluorescent in situ hybridization	SI	International System of Units
FLC	free light chain	SOC	system organ class
GGT	gamma-glutamyl transferase	SPEP	serum protein electrophoresis
HCO3	bicarbonate	TEAE	treatment-emergent adverse event
Hgb	hemoglobin	TOI	trial outcomes index
IMiD	immunomodulatory drug	TSH	thyroid stimulating hormone
IMWG	International Myeloma Working Group	TTP	time to progression
INR	international normalization ratio	ULN	upper limit of normal
IRC	Independent Review Committee	UPEP	urine protein electrophoresis
ISS	International Staging System	VGPR	very good partial response
ITT	intent-to-treat	WBC	white blood cell
LDH	lactate dehydrogenase	WHO	World Health Organization
LLN	lower limits of normal	WHO DDE	World Health Organization Drug Dictionary Enhanced
MedDRA	Medical Dictionary for Regulatory Activities	XPO1	exportin 1
mg	Milligram		

1. OVERVIEW AND INVESTIGATIONAL PLAN

1.1. STUDY DESIGN

KCP-330-012 is a Phase 2b, single-arm, open-label, multicenter study of Sd (selinexor 80 mg plus dexamethasone 20 mg), both dosed twice weekly, for each week of a four-week cycle, in patients with multiple myeloma (MM) previously treated with alkylating agents, glucocorticoids, lenalidomide, pomalidomide, bortezomib, carfilzomib, and daratumumab, and refractory to prior treatment with glucocorticoids, at least one immunomodulatory agent (IMiD), at least one proteasome inhibitor (PI), and the anti-CD38 mAb daratumumab (i.e., penta-refractory MM). Note: refractory is defined as $\leq 25\%$ response to therapy, progression during the previously described therapies, or progression within 60 days after completion of the therapy (per International Myeloma Working Group [IMWG] criteria 2016).

This study consists of two parts and will enroll approximately 210 patients overall. Part 1 (protocol V1.0-3.0) enrolled patients with both quad-refractory MM (i.e., previously treated with alkylating agents, glucocorticoids, lenalidomide, pomalidomide, bortezomib, carfilzomib, but not an anti-CD38 mAb, and refractory to prior treatment with glucocorticoids, at least one IMiD, and at least one PI) along with patients that had quad-refractory MM and whose disease was refractory to an anti-CD38 monoclonal antibody (i.e., penta-refractory MM). Part 2 (protocol V \geq 4.0) will enroll patients with penta-refractory MM only, and refractoriness to prior treatment with daratumumab (the only currently FDA approved anti-CD38 monoclonal antibody) is required.

The population for the primary efficacy analysis will contain only patients with penta-refractory MM enrolled in Part 2. Efficacy results for patients with quad-refractory MM and patients with penta-refractory MM enrolled in Part 1 will be analyzed separately. Safety analyses will be performed on the Part 2 patients with penta-refractory MM, the overall safety population of patients who received any amount of study treatment, presented together as well as separately by study part.

Patients receive oral selinexor 80 mg plus dexamethasone 20 mg (Sd), both dosed twice weekly, for each week of four-week cycles. Patients will receive treatment until progressive disease (PD), death, toxicity that cannot be managed by standard care, or withdrawal, whichever occurs first.

In select cases (e.g., for patients showing stable disease [SD] or partial response [PR] and tolerating treatment particularly well), the selinexor dose may be increased by 20 mg (up to a maximum of 100 mg per dose) after consultation with the Medical Monitor. The dose level for an individual patient may be escalated based on efficacy considerations only after a minimum of 2 cycles of study therapy. However, in no case may the dose for any patient exceed 70 mg/m². Prior to any potential dose increase, the BSA for the patient will be calculated and an individual patient's dose may not be increased if it would result in a dose > 70 mg/m².

Patient response at each time point will be assessed centrally by an Independent Review Committee (IRC) according to the IMWG response criteria (*Kumar 2016*) for MM. In Part 2, MM-specific assessments (i.e., serum protein electrophoresis [SPEP], urine protein electrophoresis [UPEP], serum/urine immunofixation, quantitative Ig levels, serum free light chain [FLC], and bone marrow aspirate) must be confirmed by a central laboratory to confirm

complete response (CR) or stringent complete response (sCR), per IMWG consensus criteria. Additional information is provided in the *IRC Charter* and *Study Manual*.

Patients may decide to discontinue study treatment for any reason. Patients who elect to discontinue study treatment should be encouraged to continue in the study so that follow-up information on disease progression, other antineoplastic therapy, symptoms and survival status may be obtained. However, patients may elect to withdraw consent and decline further participation in the trial at any time. The Investigator may remove a patient from study treatment using criteria described in Section 10.2 of Protocol V5.0.

The Investigator must determine the primary reason for a patient's discontinuation of study treatment and record this information on the electronic case report form (eCRF). Patients who are prematurely withdrawn from study treatment are not eligible to re-initiate study treatment on this protocol at a later date.

1.2. OBJECTIVES

1.2.1. Primary Objectives

Evaluate the efficacy (overall response rate [ORR] based on IRC assessment) for treatment with selinexor 80 mg plus low-dose dexamethasone (20 mg) (Sd) twice weekly (four-week cycles) in patients with penta-refractory MM previously treated with lenalidomide, pomalidomide, bortezomib, carfilzomib, and daratumumab; and refractory to prior treatment with glucocorticoids, an IMiD, a PI, and the anti-CD38 mAb daratumumab.

ORR will include patients who experience PR, very good partial response (VGPR), CR, or sCR, based on IMWG response criteria (*Kumar 2016*). The ORR for patients with penta-refractory MM in Part 2 will be compared to a minimal threshold level of 10%.

1.2.2. Secondary Objectives

The following endpoints will be analyzed separately for (a) Part 1 patients with quad-refractory MM, (b) Part 1 patients with penta-refractory MM, and (c) Part 2 patients with penta-refractory MM. Additionally, analyses of safety and tolerability will be performed on the overall population of patients from Parts 1 and 2 who received at least one dose of study treatment.

- Duration of response (DOR) = Duration from first observation of at least PR to time of PD, or death due to disease progression, whichever occurs first. DOR will be censored for death due to any causes other than disease progression.
- Clinical Benefit Rate (CBR = sCR + CR + VGPR + PR + minimal response [MR]), and duration of clinical benefit (Duration from first observation of at least MR to time of PD, or death due to disease progression, whichever occurs first. Duration of clinical benefit will be censored for death due to any cause other than disease progression.
- Disease Control Rate (DCR = CBR + SD [for a minimum of 12 weeks])
- Progression Free Survival (PFS = Duration from start of study treatment to PD or death [regardless of cause], whichever comes first)
- Time to Progression (TTP = Duration from start of study treatment to time of PD) obtained with selinexor plus dexamethasone vs. TTP on most recent prior therapy

- Time to Next Treatment (TTNT = Duration from start of study treatment to start of next anti-MM treatment or death due to disease progression, whichever occurs first)
- Overall Survival (OS = Duration from start of study treatment to death)
- Quality of Life (QoL) using the Functional Assessment of Cancer Therapy - Multiple Myeloma (FACT-MM)
- Safety and tolerability using National Cancer Institute (NCI) Common Terminology Criteria for Adverse Events (CTCAE), v 4.03.
- Describe the Pharmacokinetics (PK) properties of selinexor in this patient population (Part 1 only)

1.2.3. CCI [Redacted]

CCI [Redacted]

- [Redacted]
- [Redacted]
- [Redacted]
- [Redacted]
- [Redacted]
- [Redacted]
- [Redacted]
- [Redacted]
- [Redacted]
- [Redacted]
- [Redacted]
- [Redacted]
- [Redacted]
- [Redacted]
- [Redacted]
- [Redacted]
- [Redacted]

[Redacted]

CCI

CCI

1.4. STUDY PLAN

For each patient that signs the informed consent, the study consists of:

- Screening/baseline visit: occurs within 21 days prior to receiving the 1st dose of study treatment
- Treatment period: expected to be up to 12 months, but there is no maximum treatment duration. Patients will be treated until disease progression, death, toxicity that cannot be managed by standard care, or withdrawal from study, whichever occurs first
- Follow-up period: up to 12 months after last dose of study treatment, patients will be contacted approximately every 3 months for durability of response and survival follow-up

The End of Study (EoS) will occur when all patients have completed the 12-month follow-up period (i.e., when the last patient has expired, been followed for 12 months after last dose of study treatment, been lost to follow-up, or has withdrawn consent, whichever occurs first).

Please refer to Table 7-1 for detailed schedule of assessment and study activities.

1.5. INTERIM ANALYSIS

No interim analysis is planned for this study.

1.6. DATABASE LOCK

The primary analysis will be performed after all patients have completed the Cycle 2 MM Assessments, and will include a formal snapshot of database and analyses of efficacy, safety, and PK data. A clinical study report (CSR) will be prepared after the primary analysis. The data cut date for IRC-based MM response assessment may be later than the data cut date for other data points. All data points presented to IRC members for their assessment have been source verified.

At the time of the database snapshot for the primary analysis, the median DOR estimate may not be estimable with limited follow-up time. Therefore, an efficacy update on ORR and DOR among the Part 2 patients with penta-refractory MM will be provided before the submission of the New Drug Application (NDA) package.

The final analysis will be performed at the end of the study after all patients have completed the 12-month follow-up period (i.e., when the last patient has expired, been followed for 12 months after last dose of study treatment, been lost to follow-up, or has withdrawn consent, whichever occurs first). There will be a formal database lock and analyses of efficacy and safety data. A final CSR will be prepared summarizing the results from the full analysis.

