4. EFFICACY

Patient response at each time point will be assessed centrally by an IRC according to the IMWG response criteria (*Kumar 2016*) for MM. Unless otherwise specified, MM response assessment refers to assessment determined by IRC. The primary endpoint (ORR) is based on these IRC assessed responses in the mITT population.

Documentation of response requires two consecutive readings of the applicable disease parameter (serum M-protein, urine M-protein, serum FLC, or quantitative immunoglobulin level), performed at any time with no minimum interval required between the two readings. The date of response or PD will be assigned to the earlier date of the two independent samples, unless PD is based on an unambiguous criterion such as a new plasmacytoma lesion.

If a patient had one PD assessment but was not subsequently confirmed, unless IRC considers the progression assessment unambiguous, it is not considered a PD (*Kumar 2016*).

Unless otherwise specified, efficacy analyses will use the mITT population. Analyses for the primary efficacy endpoint of ORR and the key secondary efficacy endpoints of DOR, CBR, and duration of clinical benefit will be repeated in the other efficacy populations and additional analysis populations. If relevant, selected efficacy analyses for other efficacy endpoints will be repeated in selected additional analysis populations.

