4.2.3. Disease Control Rate (DCR)

4.2.3.1. Definition

DCR is defined as the proportion of patients who achieve SD for a minimum of 12 weeks, or better (i.e., SD for a minimum of 12 weeks, MR, PR, VGPR, CR, sCR).

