4.2.3.2. Analysis Methods

The rate of DCR and the 2-sided, exact 95% CI will be calculated using the mITT population.

As supportive analyses, DCR rate and 95% CI will be calculated:

- Using the BCLPD-ref, CLPD-ref, BCPD-ref, and CPD-ref populations respectively, if sufficient data exist

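### At the Cycle 2 snapshot, DCR needs 12 weeks of stable disease but keeps the full mITT denominator, so the primary CSR may understate it slightly

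*SAP*

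**What the plan says.** **Timing.** SAP 1.6 sets the snapshot: "The primary analysis will be performed after all patients have completed the Cycle 2 MM Assessments". In SAP Table 7-1 the full Cycle 2 myeloma panel falls on Cycle 2 Day 1 (study Day 29). Only serum FLC is repeated on Cycle 2 Day 15 (Day 43). SAP 1.6 also allows the response data to run on: "The data cut date for IRC-based MM response assessment may be later than the data cut date for other data points". It gives no length for that lag.

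**Endpoint.** SAP 4.2.3.1: "DCR is defined as the proportion of patients who achieve SD for a minimum of 12 weeks, or better". SAP 4.2.3.2: "The rate of DCR and the 2-sided, exact 95% CI will be calculated using the mITT population". The visible text sets no minimum follow-up, has no category for patients not yet evaluable, and does not say whether the 12 weeks starts at first dose or at the first SD assessment.

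**Later looks.** Before the NDA, "an efficacy update on ORR and DOR among the Part 2 patients with penta-refractory MM will be provided"; DCR is not in that update. After it comes the end-of-study analysis: "The final analysis will be performed at the end of the study after all patients have completed the 12-month follow-up period".

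**Rank.** SAP 4 names the "key secondary efficacy endpoints of DOR, CBR, and duration of clinical benefit". DCR is not among them.

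**The concern.** A patient first dosed shortly before the snapshot and still in SD is in the denominator but has not had time to enter the numerator. The SAP does not say in words that such a patient counts as not controlled. That follows from putting the 12-week definition over the full mITT population.

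The shortfall would reflect short follow-up, not loss of disease control. The exact confidence interval would not show it, because that interval describes sampling error only. SAP 1.6 recognises limited follow-up for DOR and plans an update for it, but offers nothing similar for DCR. At stake is one secondary figure in the primary CSR.

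**Working it through.** The plan states no DCR figure, so there is none to reproduce.

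**Inputs from the documents**
- mITT target 122 (Protocol synopsis, Study Numbers).
- Enrollment about 24 months (Protocol synopsis, Study Duration). The length of Part 2 alone is not stated.
- Response assessments every 28 days (SAP 4.2.5.2). Cycle 2 Day 1, Cycle 2 Day 15, Cycle 3 Day 1 and Cycle 4 Day 1 are Days 29, 43, 57 and 85.
- SD of any duration as best response in 6 of 30 Part 1 penta-refractory patients, 20% (Protocol Table 3).

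**Assumptions**
- Even accrual.
- The IRC cut is on the trigger date (zero lag).
- SD is timed from first dose, so 12 weeks is reached on Day 12 × 7 + 1 = 85.
- 10-20% of patients have SD of at least 12 weeks as best response. The upper value is a ceiling taken from Table 3, since some SD ends before week 12.

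**Formulas**
- Patients short = 122 × (85 − trigger day − lag) / accrual days
- DCR loss = (patients short / 122) × share with qualifying SD

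Accrual days are 730.5 for 24 months and 365.25 for 12 months. For Day 29 and 24 months: 122 × 56 / 730.5 = 9.4 patients, or 7.67% of 122. At shares of 10% and 20% that is 0.77 and 1.53 points.

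| Last patient at | Days short | Patients short, 24 months | DCR loss, 10-20% share | Patients short, 12 months (assumed) | DCR loss, 20% share |
|---|---|---|---|---|---|
| Day 29 | 56 | 9.4 | 0.77-1.53 | 18.7 | 3.1 |
| Day 43 | 42 | 7.0 | 0.57-1.15 | 14.0 | 2.3 |
| Day 57 | 28 | 4.7 | 0.38-0.77 | 9.4 | 1.5 |

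**Effect of a lag.** At 24 months a 28-day lag leaves 4.7 patients (Day 29) or 2.3 (Day 43), a loss of 0.19-0.77 points. The loss is nil once the lag reaches 56, 42 or 28 days for Days 29, 43 and 57.

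**If SD is timed from a first SD assessment on Day 29.** The target becomes Day 29 + 84 = 113. At 24 months and zero lag, 14.0 patients (Day 29) or 11.7 (Day 43) are short and the loss is 0.96-2.30 points. It then takes a lag of 84 or 70 days to remove it.

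**Scale.** Part 1 penta-refractory CBR (40%) plus SD (20%) suggests a DCR near 60%. 73/122 is 59.8% (exact 95% CI 50.6-68.6). With two patients not counted, 71/122 is 58.2% (48.9-67.1). The half-width at 73/122 is 9.0 points, several times the base-case loss.

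This covers the SD component only. Patients who would first reach MR or better after the cut are not counted.

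**The case against.** The strongest reply is that this is too small to matter and is largely covered elsewhere.

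- **Other endpoints describe stability.** Protocol Appendix 3 says disease stability is better conveyed by TTP, and SAP Tables 4-1 and 4-2 censor a patient in ongoing SD at the last adequate assessment. This stands. The CSR will contain measures that handle short follow-up properly. It does not correct the DCR proportion printed beside them.
- **The lag may remove it.** The Cycle 2 trigger is an earliest time, and a later IRC cut is expressly allowed. This also stands: the shortfall is conditional. But the later cut is optional and its length is not given, so the plan does not guarantee the remedy.
- **A rule may exist elsewhere.** The IRC Charter, which the SAP cites, could define SD timing. It is not available here, so this cannot be excluded.
- **The accrual pattern is assumed.** True. Only the 24-month figure is documented, and it refers to the study, not to Part 2 alone. The 12-month case shows sensitivity and is not an estimate.

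A reader might infer that DCR is certain to be understated, or seriously so. The documents do not support that: the lag is unstated, and much larger losses need a short Part 2 accrual that appears nowhere in them. A reader might also infer that the primary result is at risk. The 12-week rule has no part in the ORR definition (SAP 4.1.1) or its test (SAP 4.1.2).

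**Conclusion.** The point stands as a minor one. Followed as written, the plan gives a slightly low DCR in the primary CSR unless the IRC response cut comes about 42-56 days or more after the trigger (28 days on the Day 57 reading). Under the base-case assumptions the loss is 0.6-1.5 points, or 0.4-0.8 on the Day 57 reading. It reaches about 3 points only with an assumed 12-month accrual and a 20% share of qualifying SD.

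The bias is downward and temporary: the final analysis removes it, but no earlier planned analysis of DCR does. No hypothesis test depends on DCR.

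One part is not temporary. Until the start of the 12 weeks is defined, a patient whose SD ends between about Day 85 and Day 113 counts under one reading and not under the other, at the final analysis too.

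**What to change.** 1. Add DCR to the pre-NDA update already planned in SAP 1.6.
2. At the snapshot, flag the full-mITT DCR as immature. Beside it show DCR in all mITT patients first dosed at least 12 weeks plus the visit window (84 + 2 = 86 days) before the IRC response cut, whatever their outcome. Show CBR for the same patients, so that DCR still equals CBR plus qualifying SD. Selection is by first-dose date, not by response.
3. State in SAP 4.2.3.1 whether the 12 weeks runs from first dose or from the first SD assessment, and set the limit in item 2 to match. With a first SD assessment at about week 4, the limit becomes 16 weeks plus the window.

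**Cost.** SAP wording, an added table row and one more endpoint in an existing update. Snapshot timing, sample size and the primary test do not change. Two DCR figures must be explained, and the restricted one is slightly less precise: at a DCR near 60% the exact 95% half-width is about 9.3-9.4 points (n = 115 to 113, 24-month accrual) against 9.0 for n = 122. Delayed cycles could still leave an occasional patient in the restricted group without the Day 85 assessment; a footnote can say so.
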